#### 17.7 Procedures to account for missing or spurious data

The handling of missing data and the multiple imputation methods used has been described in section 17.4 for the primary estimand and in section 17.6 for certain sensitivity analyses of the primary outcomes analysis. Categories for reasons for missing follow-up data will be defined in the data management plan and added as a variable in the trial database.

#### 17.8 Economic evaluation

Cost-effectiveness of the intervention within the 180 day follow-up will be estimated from the perspective of health and social care services. The intervention costs will include any costs associated with training, supervision and equipment and additional consultation time to deliver the intervention. Additionally, with patient consent, we will request linked data describing secondary care attendances from 180 days prior to entry into the study until the end of follow-up in the trial (i.e. Hospital Episodes Statistics datasets for inpatient admissions, outpatient, critical care and A&E attendances). We will collect further resource use data (e.g. primary care consultations, community and residential care, out-of-pocket expenses and work-time loss due to ill health) using tailored self-report questions administered at entry into the study and at final follow-up 180 days later, requesting information about the previous 180 days. All healthcare use in the OSIRIS study will be costed using NHS and national reference costs [20, 21]. For the purpose of the economic analyses, health outcomes will be measured in qualityadjusted life years (QALYs). Health-related quality of life will be estimated using data from the EQ-5D-5L questionnaire collected at baseline, post-surgical clinic visit, 30 day follow-up after day of surgery and 180 day follow-up after index decision making episode in the OSIRIS study. EQ-5D-5L utilities will be derived using the NICE Decision

OSIRIS Protocol v2.0 20.11.2023 Page **34** of **46** 

Support Unit (DSU) tariff [22] recommended in the latest NICE guidelines for health technology assessments [23]. Mean costs and QALYs between the trial arms will be compared using separate linear mixed-effects models with a random-intercept for hospital. The following baseline covariates will be adjusted for: age, surgical procedure, Charlson co-morbidity score and hospital care costs in the 180 days prior to entry into OSIRIS or EQ-5D-5L utility at entry, respectively. Missing baseline covariate data will be accounted for using mean imputation. The two-stage bootstrap approach will be used to assess the uncertainty in cost-effectiveness.

Cost-effectiveness of the intervention over life-time horizon will combine i) data from the trial describing resources use and cost of the intervention, and ii) long-term projections of quality of life adjusted survival and healthcare costs associated with particular treatments from the decision-analytic models to project long-term effectiveness and cost-effectiveness of the OSIRIS decision support intervention: a) across the participants in the cluster trial, and b) in cohorts of high-risk patients in routine hospital care data (e.g. by level of risk, age). We will report incremental costs per QALY gained with the OSIRIS intervention, along with cost-effectives acceptability curves across values of cost-effectiveness threshold (£0 to £50,000). All future costs and health outcomes will be discounted as recommended [23]. The wider implications of the OSIRIS intervention on patients' families and society (e.g. employment, informal care needs) will be considered. A health economics analysis plan, specifying in detail the health economics analyses of the OSIRIS intervention, will be finalised and signed off prior to un-blinding the team analysing the study.

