### 5. Introduction

Far from being replaced by new drug therapies, surgical treatments are offered to more patients than ever before. This is a particular concern for the 250,000 NHS patients at high risk of post-operative complications who undergo major surgery each year [1]. These patients are older, and usually have chronic disease. Even when surgery and anaesthesia are straightforward, one in three high-risk patients still develops medical complications in the days following surgery [2]. These complications delay recovery, with prolonged hospital stays and poor functional independence once patients return home. Critically, many high-risk surgical patients never recover from these adverse effects, suffering significant reductions in long-term quality of life and survival [2, 3]. For many, surgery is not the successful treatment they hoped for. Feelings of guilt or regret over the decision to undergo surgery are commonplace [4]. Doctors recognise the urgent need to improve decision making for this patient group but clearly feel ill-equipped to tackle this [5]. This problem is becoming more frequent as surgical treatments are offered to more patients living with chronic disease.

Understandably, surgeons and anaesthetists are focused on safe and effective care during surgery and the days that follow. High-risk patients are most likely to experience life-threatening complications during this period and receive good information about these short-term risks. Meanwhile, information on long-term outcomes is mostly focused on the index disease that surgery is treating e.g. osteoarthritis, bowel cancer or vascular disease. The benefits of surgical treatment may, however, be self-limiting for high-risk patients who experience deterioration in other aspects of their health. Few doctors have the breadth of expertise, or the detailed knowledge needed to forecast every likely long-term outcome for complex surgical patients with multiple co-morbid diseases, whilst patients often have unrealistic expectations of what surgery can achieve. High-risk patients frequently consent to surgery unaware that poor long-term outcomes may completely negate the potential benefits.

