#### 6. Trial objectives

The primary trial objective is to determine the clinical and cost-effectiveness of a decision support intervention relative to best standard of care for shared decision making in reducing decision regret after surgery whilst not adversely affecting mental health-related quality of life at 180 days after the index decision making episode at which the decision to proceed or not proceed with surgery is made.

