# 12. Study procedures

12.1 Schedule of measurements for each visit

Visit	Pre-surgical /surgical clinic	Index decision making episode	Post-surgical clinic visit	Surgery	Hospital discharge	30-day follow-up after surgery ± 3 days	180-day follow-up after index decision ± 3 days
Data sources	In person and/or medical records	In person	In person or via telephone	Medical records	Medical records	Medical records and telephone interview	Medical records and telephone interview
Eligibility	×						
Informed consent	×	X¹					
Demographics	х						
NHS number, gender, date of birth, postcode	Х						
Co-morbidities	X						
EQ-5D-5L	×		Х			Х	Х
SF-12	×						Х
Decision aid		Х					
Details of planned and actual treatment		Х		Х			
SDM-Q9			$X^2$				
Health services resource use questionnaire			Х				Х
Complications						X 	
Patient vital status					Х	X 	Х
Patient discharge location					Х	X 	
Decision Regret Score							х
Follow-up interview		X 	X 			X 	х

<sup>1 If obtained before the surgical clinic, consent should be confirmed before the intervention takes place  Patient identifiable data collected for NHS Digital  Within 48h of decision making

<sup>4Where possible and appropriate
The interview can be completed either immediately after the consultation or subsequently over the phone
 Data collected from 30 days after surgery (only applicable if a patient has had surgery)

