## Post-clinic follow up

- SDM-Q-9
- Healthcare use questionnaire
- Predicted post-operative quality of life according to EQ-5D-5L

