## Follow-up data

## 30-day after date of surgery follow-up

- Patient vital status (dead/alive)
- Complications measured according to Clavien-Dindo scale (Patients who don't undergo surgery will be coded as 'not applicable'.)
- Patients discharge location
- Quality of life according to EQ-5D-5L

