#### 12.6 Intervention

This is a complex intervention, combining training to promote effective shared decision making for high-risk surgical patients (see above) together with a software-based decision support intervention. This software utilises a series of computational models developed by the OSIRIS team, which incorporates modelling of patient outcomes using NHS registry data, and patient-level information on quality of life outcomes after major surgery. Patients and doctors will use the intervention during all decision making encounters with the surgeons and other healthcare staff (e.g. anaesthetists, specialist nurses). By combining data sources from previous studies within this programme of work with NHS registry data the intervention will generate a forecast of important long-term outcomes for the patient. This forecast is presented using a clear and simple user interface with icon arrays and other patient friendly display methods to ensure it is correctly understood. Patients will be able to select and focus on outcomes of most relevance to them, whilst the intervention could highlight important outcomes which the patient might not have considered.

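### Section 17.8 feeds the post-clinic EQ-5D-5L into the within-trial QALYs, but section 12.4 describes that questionnaire as a prediction of post-operative quality of life

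*Protocol*

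**What the plan says.** Section 6 of the Protocol makes economics part of the primary objective, which is to "determine the clinical and cost-effectiveness of a decision support intervention". Section 17.8 expresses health outcomes as QALYs over the 180-day follow-up and names four sources of utility, all on the same footing: the "EQ-5D-5L questionnaire collected at baseline, post-surgical clinic visit, 30 day follow-up after day of surgery and 180 day follow-up".

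Section 12.4 (Post-clinic follow up) lists one EQ-5D-5L item: "Predicted post-operative quality of life according to EQ-5D-5L". The 30-day item in the same section reads "Quality of life according to EQ-5D-5L", and the baseline and 180-day items are worded the same way.

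The schedule in 12.1 orders its first four columns "Pre-surgical /surgical clinic Index decision making episode Post-surgical clinic visit Surgery". The third column, which despite its name comes before the operation, has a single EQ-5D-5L mark. That mark sits on the same row as the baseline, 30-day and 180-day marks, with no note that it is a prediction.

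Section 12.9 limits the 30-day interview to participants who have had surgery.

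**The concern.** A QALY weights time lived by the health experienced during that time. What a patient expects life to be like after an operation that has not yet happened does not describe the interval between the clinic and the next assessment. For a patient who decides against surgery, a predicted post-operative state is not even defined.

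The item is also exposed to treatment. It is completed after the aid has been used, and section 12.6 says that "the intervention will generate a forecast of important long-term outcomes for the patient". Section 5 gives part of the rationale: "patients often have unrealistic expectations of what surgery can achieve". It is reasonable to expect the aid to move patients' predictions, in which case the two arms could report different predicted utilities while living in identical health. That difference would pass into the incremental QALYs. Section 17.8 adjusts QALYs for EQ-5D-5L utility at entry, but this cannot remove a difference that arises after allocation.

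At stake is the 180-day cost-effectiveness comparison.

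**Working it through.** The protocol states no expected utility, QALY figure or QALY formula, so there is nothing of its own to reproduce. The check has two parts.

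**1. The sections side by side**

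| Assessment | Section 12.4 | Section 17.8 |
|---|---|---|
| Baseline | quality of life | QALY input |
| Post-clinic | predicted post-operative quality of life | QALY input |
| 30 days after surgery | quality of life | QALY input |
| 180 days after index decision | quality of life | QALY input |

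Only the post-clinic row differs in 12.4, and 17.8 makes no exception for it. Because 12.1 has one EQ-5D-5L mark at that visit, the documents show no second, current-health questionnaire there to which 17.8 could be referring.

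**2. Illustrative size**

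Assumptions, none of them from the protocol:
- The QALY is the trapezoidal area under the utility curve.
- Baseline is at day 0.
- The 30-day visit falls between day 45 and day 120 (surgery at day 15 to day 90).
- Real health is identical in the two arms.

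Let baseline be at t0, the post-clinic item at t1 and the next real measurement at t2. The post-clinic utility enters two trapezoids, so its weight in years is

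[(t1 − t0)/2 + (t2 − t1)/2] / 365.25 = (t2 − t0) / (2 × 365.25).

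The exact day of the post-clinic item cancels. A between-arm difference d in predicted utility produces a spurious QALY difference of weight × d.

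| Next real measurement | Weight (years) | d = 0.05 | d = 0.10 |
|---|---|---|---|
| Day 45 (operated) | 45/730.5 = 0.0616 | 0.0031 | 0.0062 |
| Day 60 (operated) | 60/730.5 = 0.0821 | 0.0041 | 0.0082 |
| Day 120 (operated) | 120/730.5 = 0.1643 | 0.0082 | 0.0164 |
| Day 180 (no surgery, no 30-day visit) | 180/730.5 = 0.2464 | 0.0123 | 0.0246 |

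The last row applies only if patients without surgery complete the item. With baseline 14 days before the index decision, the d = 0.05 figures become 0.0040 (day 45), 0.0092 (day 120) and 0.0133 (day 180).

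The level is affected even when the arms do not differ. Take a patient with utility 0.60 at baseline, 0.60 at day 60 and 0.70 at day 180, who predicts 0.80 at day 2:
- With the prediction: (2 × 0.70 + 58 × 0.70 + 120 × 0.65)/365.25 = 120/365.25 = 0.329.
- Without it: (60 × 0.60 + 120 × 0.65)/365.25 = 114/365.25 = 0.312.

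If the prediction is left out, its weight is zero and so is the spurious difference.

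**The case against.** The strongest reply is that the fault may lie in 12.4 and not in 17.8. The schedule marks an ordinary EQ-5D-5L at that visit, 17.8 treats it as one, and only 12.4 calls it a prediction. If the form asks about current health, the time point is valid, and striking it out would discard the only utility between baseline and day 180 for patients without surgery. This stands: the documents do not show what the form asks, so unconditional deletion is not supported.

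A second reply is that 17.8 leaves detail to a health economics analysis plan, to be signed off before unblinding, which could exclude the value. That offers an opportunity to correct the problem but does not answer it. The protocol already names this visit as a QALY input, so a plan that follows the protocol inherits the problem and one that drops the visit departs from it.

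Some stronger readings are tempting but go beyond the documents:
- **That the aid lowers predictions and so biases QALYs against the intervention.** No effect on predicted EQ-5D-5L is stated. Lower predictions after the aid would count against it and higher ones in its favour.
- **That the item is taken within 48 hours of the decision.** Section 6.2 attaches that window to the shared decision-making questionnaire. The EQ-5D-5L merely shares its column in 12.1.
- **That the error can be priced at the upper cost-effectiveness threshold.** The £0 to £50,000 range appears in the lifetime-horizon paragraph of 17.8. There the named trial inputs are resource use and intervention cost, and quality-adjusted survival comes from decision-analytic models. The effect shown here is confined to the 180-day comparison.

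**Conclusion.** The conflict is real. Read as written, 17.8 counts a prediction made after the intervention as health experienced. This could bias the 180-day incremental QALYs in either direction.

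For a 0.05 between-arm difference in predicted utility, the spurious difference is about 0.003 to 0.008 QALY in operated patients and about 0.012 in patients without surgery who complete the item. These figures rest on the trapezoidal rule, the assumed visit days and the assumed utility difference. They show how the error scales and do not estimate what the trial will produce.

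The declaration of clinical effectiveness rests on decision regret and MCS (section 17.4) and is untouched, as is the secondary EQ-5D-5L outcome at 180 days. The point still needs correcting, because cost-effectiveness is in the primary objective and the error is avoidable.

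**What to change.** Establish from the case report form what the post-clinic EQ-5D-5L asks, then bring sections 12.1, 12.4 and 17.8 into line before the health economics analysis plan is signed off.

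- **If it is a prediction, as 12.4 states:** remove the post-surgical clinic visit from the QALY inputs in 17.8 and in the health economics analysis plan. Compute QALYs from the baseline, 30-day and 180-day responses, label the item as predicted in 12.1, and report it only as a measure of expectations. Patients without surgery then contribute baseline and 180-day values only.
- **If it records current health:** correct the wording in 12.4 and keep the time point.

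Either route costs a phrase or two in the protocol and the matching line in the economics plan. Neither needs new data.

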#### 18. Data handling and record keeping

#### 18.1 Source data and source documents

Source data is defined as all information in original patient records and certified copies of original records of clinical findings, observations, or other activities in a clinical trial necessary for the reconstruction and evaluation of the clinical investigation. Source data are contained in source documents (original records or certified copies). Only members of the direct care team are entitled to have access to patients' medical records. Direct access will be granted to authorised representatives from the sponsor, host institution, and the regulatory authorities to permit study-related monitoring, audits, and inspections.

OSIRIS Protocol v2.0 20.11.2023 Page **35** of **46** 

#### 18.2 Case report forms

A summary of the data collection points and times can be found in section 12.1 Research staff at each hospital will be responsible for the completion of the electronic case report form for the duration of the study. The electronic case report form will be custom designed by Queen Mary University of London and will be hosted on a secure server. A requirement specifications document will be created detailing these aspects of the database. Sites will be provided with a paper data collection tool that matches the electronic case report form however, it is not compulsory to complete this. The electronic patient questionnaire will act as source data for patient reported outcomes collecting during the 30 day and 180 day follow-up. Patient's medical notes will act as source for the rest of the data. It is expected that the exact source data list will vary by site. A site agreement will be in place at each site.

# 18.3 Transferring and transporting data

All data must be handled in accordance with the Data Protection Act (2018) and General Data Protection Regulations. Identifiable information must not be stored or transported on any portable device (e.g., laptops, memory sticks, CD / DVDs) unless it is encrypted. Similarly, data must not be sent electronically if it is not subject to end-to-end encryption. In the event that Patient Identifiable Data needs to be transferred between authorized users, this will occur by email [contact] [contact] accounts.

For registry linkage QMUL will apply to NHS digital for HES and Civil Registrations (Deaths) data. Following approvals for the proposed linkage, QMUL will send the Study ID, NHS Number, Forename, Surname, Sex, Date of Birth and Postcode to NHS Digital to link the cohort to HES and Civil Registrations data. NHS digital will send the relevant data for QMUL to be perform the linkage data to the trial data based on the Study ID.

#### 18.4 Data management

A full data management plan will be developed to describe in detail the methods of data management. All participant data collected will be entered onto a secure electronic data entry system. The site Principal Investigators will oversee and be responsible for data collection, quality and recording. Collection of data can be delegated (as per the Delegation Log) by the site Principal Investigators to qualified members of the research team. Data entered onto the secure electronic data entry system will undergo validation

OSIRIS Protocol v2.0 20.11.2023 Page **36** of **46** 

checks for completeness, accuracy and consistency of data. The electronic storage will be located on a restricted area of the file server. Submitted data will be stored securely against unauthorised manipulation and accidental loss. Queries on incomplete, inaccurate or inconsistent data will be sent to the local research team at participating sites for resolution. Security of the electronic data entry system is maintained through user names and individual permissions approved centrally by the OSRIS trial mangers. Central back-up procedures are in place. Storage and handling of confidential trial data and documents will be in accordance with the Data Protection Act (2018) and General Data Protection Regulations. Representatives of the trial management team will require access to patient notes for quality assurance purposes and source data verification, but patients' confidentiality will be respected at all times. In the case of special problems and/or competent authority queries, it is also necessary to have access to the complete trial records, provided that patient confidentiality is protected.

## 18.5 Confidentiality

The Chief Investigator will be the data custodian for all data generated during the study. The Chief Investigator and the study team will ensure that all participants' identities are protected at every stage of the study. The patient's NHS Number, gender, date of birth and postcode will be collected at randomisation through the trial database and sent to NHS Digital to allow tracing through national records. The personal data recorded on all documents will be regarded as confidential.

The Principal Investigator is responsible for protecting the identity of participants at their site. Participants will be referred to only by their unique study identifier whenever data is transferred outside of the site, and in all correspondence between the site and the coordinating centre, co-investigators, Sponsor, or anyone associated with the study. No participants will be individually identifiable from any publications resulting from the study.

Information regarding study participants will be kept confidential and managed in accordance with the Data Protection Act (2018), the UK Policy Framework for Health and Social Care and Research Ethics Committee approval. All study data will be stored in line with the Medicines for Human Use (Clinical Trials) Regulations 2004 and subsequent amendments and the Data Protection Act. Study data will be archived in line with the Medicines for Human Use (Clinical Trials) Regulations 2004 and all subsequent amendments, and as defined in the Sponsor SOP for archiving.

OSIRIS Protocol v2.0 20.11.2023 Page **37** of **46** 

## 19. Participants

A screening log will be maintained throughout the study. Usually this includes the potential participant's initials to allow their identification by relevant site staff. Once the participant has completed screening procedures and enrolled onto the study, they must be allocated a unique study identifier generated by the OSRIS trial database.

The participant's full name, date of birth, hospital number and NHS number (UK) will be entered on to the secure data entry web portal to allow tracing through national records. The personal data recorded on all documents will be regarded as confidential. All participant related trial documents are confidential and must be stored securely at each hospital (e.g. participant consent forms). The Principal Investigator must ensure the patient's confidentiality is maintained at all times. The Sponsor will ensure that all participating partner organisations will maintain the confidentiality of all subject data and will not reproduce or disclose any information by which subjects could be identified, other than reporting of serious adverse events. Data will be stored and handled in accordance with the Data Protection Act 2018 (UK). In the event that patient identifiable data needs to be transferred between authorised users, this will occur by email [contact] [contact] accounts in the UK

